**Prior/Concomitant Therapy**

10. Treatment initiation or change of dose of ACE inhibitors or ARBs in the 4 weeks before the screening.

**Prior/Concurrent Clinical Trial Experience**

11. Current participation in an interventional study, in which the participant received any drug within 90 days before the Screening visit.

**5.3 Lifestyle Considerations**

No lifestyle restrictions are required during any of the study periods.

**5.4 Screen Failures**

A screen failure occurs when a participant who consents to participate in the clinical study is not subsequently entered in the study. A minimal set of screen failure information is required to ensure transparent reporting of screen failure participants to meet the Consolidated Standards of Reporting Trials publishing requirements and to respond to queries from regulatory authorities. Minimal information includes demography, screen failure details, eligibility criteria, and any serious adverse event (SAE).

Individuals who do not meet the criteria for participation in this study (screen failure) may be rescreened, at Investigator's discretion. Rescreened participants should be assigned a new identification number for every screening/rescreening event. For rescreened participants, the same previously signed ICF should be used unless more than 30 days have passed since the first ICF was signed. In these cases, another ICF must be signed.

## 6.0 STUDY INTERVENTION(S) AND CONCOMITANT THERAPY

Study intervention is defined as any investigational intervention(s), marketed product(s), placebo, or medical device(s) intended to be administered to a study participant according to the study protocol.

### 6.1 Study Intervention(s) Administered

The study has a single-arm. First, all participants will receive 2 doses of Fabrazyme® with approximately 14 days between them, and afterwards all participants will switch treatment and receive AGA BETA BS for 54 weeks. Details of both medications are provided in [Table 4](#).

**Table 4 Study Intervention(s) Administered**

Intervention Label	Fabrazyme®	AGA BETA BS
Intervention Name	Recombinant human alpha-galactosidase A (agalsidase beta)	Recombinant human alpha-galactosidase A (agalsidase beta)
Intervention Description	Agalsidase beta from Sanofi Genzyme	Agalsidase beta from Biosidus
Type	Biological	Biological
Dose Formulation	Lyophilized powder for reconstitution	Lyophilized powder for reconstitution
Unit Dose Strength(s)	35 mg and/or 5 mg	35 mg and/or 5 mg
Dosage Level(s)	1 mg/kg of body mass every 2 weeks	1 mg/kg of body mass every 2 weeks
Route of Administration	IV infusion	IV infusion
Use	Lead-in intervention/background intervention (study period 1)	Experimental intervention (study period 2)
IMP and NIMP/AMP	IMP	IMP
Sourcing	Provided centrally by the Sponsor	Provided centrally by the Sponsor
Packaging and Labeling	Study intervention will be provided in cartons containing 1, 5, or 10 single-use glass vials with 35 mg or 5 mg of agalsidase beta. Each carton will be labeled as required per country requirement.	Study intervention will be provided in cartons containing 1, 5, or 10 single-use glass vials with 35 mg or 5 mg of agalsidase beta. Each carton will be labeled as required per country requirement.

Abbreviations: AMP=auxiliary medicinal products; IMP=investigational medical product; IV=intravenous; NIMP=noninvestigational medical product.

### 6.2 Preparation, Handling, Storage, Administration and Accountability

#### 6.2.1 Packaging and Labeling

The study interventions will be provided by the Sponsor in sufficient quantity to supply the treatment of all participants included in the trial.

Each carton of study intervention will be labeled per local requirements and this label must remain affixed to the carton. Upon receipt, study treatment should be stored as specified on the label and kept in a secure location. The two investigational drugs (Fabrazyme® and AGA BETA BS) will be distinguishable. Study intervention will only be used for the conduct of this study.

### **6.2.2 Storage and Accountability**

Both investigational drugs must be stored at 2°C to 8°C (36°F to 46°F). All investigational product provided by the Sponsor must be stored according to the storage conditions on the clinical label. The investigational products are for investigational use only and are to be used only within the context of this study. The study treatment supplied for this study must be maintained under adequate security and stored under the conditions specified on the label until dispensed for participant use or returned to the Sponsor, as appropriate. The Investigator or designee must confirm appropriate temperature conditions have been maintained during transit for all study treatment received, and any discrepancies are reported and resolved before use of the study treatment.

Only participants enrolled in the study may receive study intervention, and only authorized study site staff may supply or administer study intervention. All study intervention must be stored in a secure, environmentally controlled, and monitored (manual or automated) area in accordance with the labeled storage conditions with access limited to the Investigator and authorized study site staff.

The Investigator, institution, or the head of the medical institution (where applicable) is responsible for study intervention accountability, reconciliation, and record maintenance (ie, receipt, reconciliation, and final disposition records).

The Investigator, a member of the study site staff, or the institution's pharmacist must maintain an adequate record of the receipt and distribution of all study intervention using the Drug Accountability Form. These forms must be available for inspection at any time.

All unused study interventions must be returned to the Sponsor at the end of the trial in accordance with current legislation.

### **6.2.3 Reconstitution and Administration**

Guidance about reconstitution and dose preparation for Fabrazyme® and AGA BETA BS and the necessary materials for the infusion are provided in Appendix 2 (Section 10.2).

For both investigational drugs, the initial IV infusion rate will be no more than 0.25 mg/minute (15 mg/hour). The infusion rate may be slowed in the event of IARs. After participant tolerance to the infusion is well established, the infusion rate may be increased gradually in increments of 0.05 to 0.08 mg/minute (increments of 3 to 5 mg/hour) with each

subsequent infusion. For participants weighing  $\geq 30$  kg, the administration duration should not be less than 1.5 hours (based on individual participant tolerability).

### **6.3 Measures to Minimize Bias: Randomization and Blinding**

This is a nonrandomized, open-label study. There are no stratification factors in this study.

At the Screening visit, all participants who consent will be assigned a unique identification number using a trial supply management system. For participants who do not meet the study selection criteria, the site personnel must log on to the system and identify the participant as a screen failure. Each participant will be assigned only one identification number. Identification numbers must not be reused for different participants. Rescreened participants should be assigned a new identification number for every screening/rescreening event.

Participants who are enrolled will retain their identification numbers assigned at the Screening visit throughout the study. Upon receipt of study treatment, the site will acknowledge receipt in the system.

### **6.4 Study Intervention Compliance**

Participants will be dosed at the study site, directly from the Investigator or designee. The date and time of start of each infusion, as well as the dose and total volume infused, will be recorded in the source documents.

The prescribed dosage, timing, and mode of administration may not be changed. Any departures from the intended regimen must be recorded in the electronic case report form (eCRF).

Noncompliance is defined as taking less than 80% of study treatment during any evaluation period (visit to visit).

### **6.5 Participants showing poor compliance as assessed by appointments and/or visits attendance for their drug infusions must be counseled on the importance of good compliance to the trial dosing regimen. Dose Modification**

Dose modifications are not planned or allowed in this study.

Any dose deviation must be recorded in the eCRF.

In the event of a life-threatening reaction, including anaphylactic or severe allergic reactions, AGA BETA BS will be discontinued, and necessary emergency treatment will be initiated.

## **6.6 Continued Access to Study Intervention After the End of the Study**

Following ANMAT Disposition N°6677/10, the Sponsor will grant participants who have completed all the study visits and interventions, including all the AGA BETA BS IV infusions, access to the intervention that has been beneficial and medical follow-up, according to individual medical judgment, or to an alternative intervention until access to it is guaranteed by any other means.

## **6.7 Treatment of Overdose**

The Sponsor does not recommend specific treatment for an overdose. There have been no reports of overdose with agalsidase beta. In clinical trials, participants received doses up to 3.0 mg/kg body weight.

In the event of an overdose, the Investigator should:

- Contact Biosidus' pharmacovigilance department immediately.
- Evaluate the participant to determine, in consultation with the Biosidus' pharmacovigilance department, whether study intervention should be interrupted or whether the dose should be reduced.
- Closely monitor the participant for any AE/SAE and laboratory abnormalities until study intervention can no longer be detected systemically (at least 12 hours).
- Document the quantity of the excess dose as well as the duration of the overdose.

## **6.8 Concomitant Therapy**

Any medication or vaccine (including over-the-counter or prescription medicines, recreational drugs, vitamins, and/or herbal supplements) that the participant is receiving at the time of enrollment or receives during the study must be recorded on the eCRF along with:

- Reason for use
- Dates of administration including start and end dates
- Dosage information including dose and frequency
- For vaccines (if applicable) include brand name and manufacturer (plus lot number, if available)

The participant will receive a diary to record any concomitant medication that he or she may use during the study. The delivery of the diary to the participant and its collection for evaluation is described in the SoA (Section 1.3). The participant must be instructed to take the diary with them to each medical visit and each infusion appointment for evaluation. All information collected in the diary must be recorded on the eCRF.

Any questions regarding concomitant or prior therapy should be raised to the Sponsor's emergency contact.

Non-investigational pretreatment with antihistamine will be administered to avoid IARs at the Investigator's discretion in period 1 but will be compulsory during the first 2 infusions in period 2. The antihistamine pretreatment will also be at Investigator's discretion on the following infusions. This medication will be provided by Biosidus to study sites and is described in [Table 5](#). When used, the antihistamine medication must be recorded as concomitant medication.

**Table 5 Noninvestigational Antihistaminic Pretreatment**

Drug Name	Loratadine
Study Treatment Name:	Loratadine
Type	Drug
Dosage Formulation:	Tablet
Unit Dose Strength(s)/Dosage Level(s):	10 mg
Route of Administration	Oral
Dosing Instructions:	1 tablet 1-2 hours before infusions
Packaging and Labeling	As required per country requirement
Manufacturer	Any approved and commercially available formulation will be used

Other medications such as antipyretic and/or corticosteroid may be administered at the Investigator's discretion to avoid or manage IARs in participants who had experienced them during agalsidase beta treatment or those who developed them during the trial. The selection of pretreatment medication and dose should be based on the participant's age, weight, and severity of the reaction. The time of administration should be based on the onset of action of the medication selected. All medications administered as pretreatment or to manage IARs must be recorded as concomitant medication on the eCRF.

### 6.8.1 Prohibited and Allowed Concomitant Medications

There are no prohibited medications during the trial. However, use of drugs that increase thrombosis risk, such as contraceptives, should be made with special caution and after a risk benefit assessment performed by the Investigator in each case, since they may theoretically additionally increase the risk of transient ischemic attack/cerebrovascular accident in females with FD.

Vaccination with live vaccines while on study is prohibited. Administration of inactivated vaccines is allowed (eg, inactivated influenza vaccines or severe acute respiratory syndrome coronavirus 2 vaccines).

Antiproteinuric drugs and pain killers are allowed as long as they haven't been started or the dose changed in the 4 weeks before screening (refer to inclusion criterion number [12](#) and

exclusion criteria number 10). Dose adjustments in these medications must be reported to the Investigator and recorded in the eCRF.

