**Table 3 Study Objectives and Corresponding Endpoints**

Objectives	Endpoints
Primary	

 
The primary objective of the study is to evaluate the equivalence in efficacy between AGA BETA BS and Fabrazyme® after 6 months of treatment in participants with Fabry disease previously stabilized with Fabrazyme, by measuring disease biomarker.
 
	
 
Mean serum Lyso-Gb3 marker ratio after 26 weeks of treatment, defined as plasma level of the marker Lyso-Gb3 after 26 weeks (6 months) divided by plasma level of the marker Lyso-Gb3 at baseline.
 

Secondary	

 
To evaluate the difference in efficacy between AGA BETA BS and Fabrazyme® after 1 year of treatment in participants with Fabry disease previously stabilized with Fabrazyme®, by measuring disease biomarker.
 
	
 
Mean serum Lyso-Gb3 marker ratio after 54 weeks of treatment, defined as plasma level of the marker Lyso-Gb3 after 54 weeks (12 months) divided by plasma level of the marker Lyso-Gb3 at baseline.
 

 
To compare the pain severity before and after the treatment with AGA BETA BS in participants with Fabry disease previously stabilized with Fabrazyme®, as measured by the BPI-short form.
 
	
 
Change from baseline in pain severity as assessed by BPI-short form pain severity items scores after 26 and 54 weeks of treatment.
 

 
To compare the impact of pain on daily functions before and after the treatment with AGA BETA BS in participants with Fabry disease previously stabilized with Fabrazyme®, as measured by the BPI-short form.
 
	
 
Change from baseline in pain interference as assessed by BPI-short form pain interference items scores after 26 and 54 weeks of treatment.
 

 
To compare the participants' perception of their own health before and after the treatment with AGA BETA BS in participants with Fabry disease previously stabilized with Fabrazyme®, as measured by the SF-36.
 
	
 
Change from baseline in SF-36 scores after 26 and 54 weeks of treatment.
 

Safety	

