#### Type of Participant and Characteristics

8. Confirmed previous diagnosis of FD.
  - a) Women: preferably present genetic testing showing pathogenic *GLA* mutation consistent with FD at screening.

- b) Men: preferably present leukocyte  $\alpha$ -Gal A activity below normal range and/ or pathogenic *GLA* mutation consistent with FD at screening.
  - c) Male with classic FD phenotype, female with classic FD and men with late onset may be included.
9. Participants who have been on stable Fabrazyme® treatment for at least 6 months prior to Baseline visit.
  10. Patients that in the last 3 months before the baseline visit have been receiving  $\geq 80\%$  of Fabrazyme®'s labeled dose/kg, this calculation includes both infusions provided by Biosidus during the Lead-in period.
  11. Disease status considered clinically stabilized, at Investigators' discretion.
  12. Estimated glomerular filtration rate (eGFR)  $\geq 45$  mL/minute/1.73 m^2 by CKD-EPI equation at Screening visit.
  13. If receiving pain killers, angiotensin-converting enzyme (ACE) inhibitors or angiotensin II receptor blockers (ARBs), participants must be in a stable dose for  $\geq 4$  weeks.

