### **8.2.2 Brief Pain Inventory-Short Form**

Pain severity and impact of pain on daily functions will be assessed by Brief Pain Inventory (BPI)-short form questionnaire.

The BPI-short form is a self-report measure that has, over time, become a standard for the assessment of pain and its impact. The BPI-short form uses a 24-hour recall period for 9 questions:

- Questions number 1 and 2 are about existence and location of pain.
- Questions number 3 to 6 correspond to pain severity items (pain rated on 0 - 10 scales at its “worst”, “least”, “average”, and “now”).
- Questions number 7 and 8 are about medications and amount of pain relief.
- Question 9 is divided into 7 others (from A to G), which correspond to pain interference items (rated on 0 - 10 scales how much pain has interfered with general activity, walking ability, normal work, mood, enjoyment of life, relations with others, and sleep).

Despite the participant answering the questionnaire in full, the questions 1, 2, 7, and 8 will not be evaluated as an endpoint in this trial.

Sufficient copies of the questionnaire in the Spanish language will be provided to the study sites by the Sponsor. Participants should be instructed to complete the entire questionnaire at the site, when applicable. The Investigator must present the questionnaire to the participant, explain its purpose, give the participant time to read the questionnaire, and ensure that the participant understands how to respond. Immediately after filled, the questionnaire must then be reviewed by study site personnel to ensure that all questions have been properly answered. If partial completion is detected, study site personnel must return the same questionnaire to the participant to have it fully completed.

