### 16.3.1 Analysis of Secondary Efficacy Endpoints

- Mean serum Lyso-Gb3 marker ratio after 54 weeks of treatment will be analyzed in an analogous way to the primary endpoint. No equivalence testing will be performed. Additionally, p-value will be presented for secondary efficacy analysis. Analysis will be based on both ITT population and PP Population.
- Pain severity and impact of pain on daily functions will be assessed through BPI Questionnaire based on the methods provided in [Appendix 3 \(BPI\)](#). Endpoint will be evaluated for average scores, across each of the domain item (Pain severity and Pain interference items) and descriptive statistics will be presented using actual and change from baseline after 26 weeks and 54 weeks of treatment for ITT Population.
- The change in health perception before and after treatment with AGA BETA BS in participants with FD previously stabilized with Fabrazyme® will be measured by the Rand -36. Descriptive statistics will be presented using actual and change from baseline data for Rand -36 scores at week 26 and week 54 for ITT Population. Additionally, Scores will be classified into different domain items namely physical functioning, Bodily Pain, general health, vitality, social functioning, role physical, Role Emotional and Mental health based on methods provided in [appendix \(Rand-36\)](#).

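### The BPI tables do not use the recorded analgesic changes, so they cannot separate stable pain from pain held stable by more analgesia

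*Protocol*

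**What the plan says.** **At entry.** Inclusion criterion 13 (Protocol 5.1) covers painkillers, ACE inhibitors and ARBs: "participants must be in a stable dose for" at least 4 weeks. Protocol 6.8.1 adds: "Antiproteinuric drugs and pain killers are allowed as long as they haven't been started or the dose changed in the 4 weeks before screening".

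**After entry.** The same section states: "There are no prohibited medications during the trial", with live vaccines as the only exception. On-study changes are expected: "Dose adjustments in these medications must be reported to the Investigator and recorded in the eCRF". Protocol 6.8 requires every medication to be recorded with its reason, start and end dates, dose and frequency.

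**The endpoint.** One secondary objective in Protocol Table 3 is "To compare the pain severity before and after the treatment with AGA BETA BS in participants with Fabry disease previously stabilized with Fabrazyme". A parallel objective covers pain interference.

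**The analysis.** In SAP 16.3.1, "descriptive statistics will be presented using actual and change from baseline after 26 weeks and 54 weeks of treatment for ITT Population". Protocol 9.2.3 says the same in substance. The two scores come from items 3 to 6 and 9A to 9G (SAP Appendix 3). Questions 7 and 8 of the BPI ask about medication and relief, but Protocol 8.2.2 states that "the questions 1, 2, 7, and 8 will not be evaluated as an endpoint in this trial".

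**The concern.** The plan treats analgesic dose as something that can distort the pain comparison at entry, and controls it there. After Day 1 that control stops, and the analysis does not take over from it.

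If pain worsens after the switch and analgesics are raised in response, the BPI change moves toward zero. In a switch study, no change is the favourable reading. There is no concurrent arm in which the same thing could happen and cancel out. What is at stake is the interpretation of two supportive secondary objectives, not the primary conclusion.

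**Working it through.** The documents give no expected BPI change, SD, margin or sample size for pain, so there is no plan figure to reproduce. The check is to follow an analgesic change through the plan and see whether it reaches a BPI table.

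| Where | What it provides | Reaches the BPI summary? |
|---|---|---|
| Protocol 6.8, 6.8.1 | Drug, reason, dose and dates recorded; changes permitted | Collected, not carried forward |
| Protocol 8.2.2 | BPI questions 7 and 8 collected | No, excluded from the endpoints |
| SAP 7.1 | Covariates and factors: not applicable | No |
| SAP 16.2.1 | Intercurrent events: primary variable only, not applicable | No |
| SAP 13, table | Counts by ATC level 3 and preferred name; drugs continued from before the switch pooled with drugs started after it | No; a dose increase in a continuing analgesic leaves the counts unchanged |
| SAP 13, listing | By-patient prior and concomitant medication, ITT | Only if matched by hand |
| SAP 16.3.1 | Observed values and change from baseline, ITT | Uses the scores alone |

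No planned summary links analgesic change to BPI.

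**Illustration on assumed inputs.** Let a share *p* of participants worsen by *w* points on the 0 to 10 scale, let added analgesia hide a fraction *r* of that worsening, and let everyone else be unchanged.

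- Reported mean change = *p* × *w* × (1 − *r*).
- With *p* = 0.25 and *w* = 2: 0.25 × 2 × 1 = 0.50 at *r* = 0; 0.25 × 2 × 0.5 = 0.25 at *r* = 0.5; and 0.00 at *r* = 1.
- Over *p* = 0.10 to 0.50 and *w* = 1 to 3, true mean worsening runs from 0.10 × 1 = 0.10 to 0.50 × 3 = 1.50. It is reported as 0.05 to 0.75 at *r* = 0.5 and as 0 at *r* = 1.

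**Comparing ways to present it.** Take 20 participants, of whom 4 worsen by 2 points and escalate, with half the worsening hidden (again assumed).

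- True mean worsening: 4 × 2 / 20 = 0.40.
- Planned summary: 4 × 1 / 20 = 0.20.
- Scores after escalation set aside: the other 16 show 0.00, further from the truth than the planned summary.
- By category: 4 of 20 (20%) started or increased, mean change 1.00; 16 of 20 (80%) no change in analgesic, mean change 0.00; overall 0.20. If all the worsening were hidden, the 20% would still be visible.

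**The case against.** The strongest reply is that the information is not lost. Protocol 9.2.1 promises by-patient listings of all collected data. SAP 6 and 13 plan listings of raw and derived variables and of medications, the latter for ITT, which is also the BPI population. With about 20 participants, a reader could match them. Worsening pain can also surface as an adverse event, because Protocol 10.5.1 counts exacerbation of a pre-existing condition and clinical consequences of lost efficacy that meet the definition. This stands. A reader might infer that analgesic escalation would be undetectable, and the documents do not support that. What is missing is a planned, linked summary.

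Second, summarising scores regardless of medication is a legitimate treatment-policy approach. That also stands, and the overall summary should stay. It is more informative when shown with how much the medication changed.

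Third, the direction is not fixed. Dose adjustments include reductions, which would push BPI the other way. A reader might infer a bias that always favours AGA BETA BS. The documents support only the possibility of one.

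Fourth, not every analgesic start signals lost control of Fabry pain. Protocol 6.8 and 8.4.6 allow antipyretics, and 8.4.6 also NSAIDs, around infusion reactions, and these are recorded as concomitant medication. A category that ignored the reason for use would be misleading.

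**Conclusion.** The point holds as a limitation of the planned summary tables. Analgesic changes after entry are permitted and recorded, the BPI tables do not use them, and the concomitant-medication table cannot fill the gap.

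The size of any bias cannot be derived from the documents. They give no escalation rate, no baseline BPI and no effect of analgesics on the score, so the figures in the working show the mechanism and are not estimates. If baseline scores are low in these clinically stabilised participants, the scope for masking is smaller.

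A reader might go on to infer that the biosimilarity conclusion is at risk. It is not: equivalence rests on the Lyso-Gb3 ratio (SAP 16.2.2), and the BPI has no test, margin or rule by which pain is declared unchanged. This is a worthwhile low-cost improvement, not a defect in the main analysis.

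**What to change.** In SAP 16.3.1, before database lock:

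1. Derive an analgesic-change category at Weeks 26 and 54 relative to Day 1: none; decreased or stopped; started or increased. Use the recorded reason for use, so that drugs given for infusion reactions or short unrelated complaints are not counted.
2. Show n (%) per category in each BPI table, and BPI change by category beside the planned overall ITT summary.
3. Do not add an analysis that sets aside scores after escalation, because it removes the participants who lost pain control.
4. Optionally, show the same kind of category for ACE inhibitor and ARB changes in the urine albumin-creatinine table.

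Two nearby passages need reconciling in the same revision. Protocol 6.8.1 cites inclusion criterion 12 (eGFR) for the painkiller rule that stands in criterion 13. SAP Appendix 3 plans BPI totals and averages across all nine items, although Protocol 8.2.2 keeps four of those questions out of the endpoints.

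The cost is one derived variable and some extra table rows, from data already collected. The cells will be small and can only be read descriptively. No change to permitted treatment is proposed.
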